
Role of this analysis plan

To better understand the mechanism of action of TMS, and of any putative benefit of cgitBS over standard repetitive TMS, we will examine a set of hypotheses derived from prior literature. Here, we describe the spectroscopic processing and statistical analysis plan.

The main study rationale is to assess whether clinical response to treatment is associated with GABA changes in the DLPFC.

Definitions of measures

- *Clinical improvement*
Mean change in depression measure from baseline (17-item HDRS total score as primary measure); changes from baseline in BDI, QIDS-SR-16, PHQ-9 and GAD-7 will be used for exploratory analyses only)
- *Treatment response*
Reduction in depression measure (17-item HDRS total score) of 50% or greater compared to baseline
- *Metabolite ratios*

GABA levels relative to Cr (GABA+/Cr), Glx levels relative to Cr (Glx/Cr) and GABA levels relative to Glx (GABA+/Glx as no macromolecule suppression). Glx and Cr will be estimated from non-edited spectra.

Primary hypotheses

1. Changes in depression symptoms on 17-item HDRS (16 weeks versus baseline) will be associated with change in GABA+/Cr between baseline and 16 weeks (post minus pre-treatment) in both treatment groups with increase in GABA+/Cr expected to be associated with decrease of HDRS (improvement).
2. Changes in depression symptoms on 17-item HDRS (26 weeks versus baseline) will be associated with change in GABA+/Cr between baseline and 16 weeks (post minus pre-treatment) in both treatment groups with increase in GABA+/Cr expected to be associated with decrease of HDRS (improvement).
3. Greater clinical improvement on 17-item HDRS (16 and 26-week vs baseline) will be associated with lower GABA+/Cr at baseline across both treatment groups.

Secondary hypotheses

1. GABA+/Cr will be increased after treatment compared to baseline for treatment responders across both treatment groups (a) and (b) GABA+/Cr increase will be higher in responders than in non-responders.
2. GABA+/Cr increase will be higher in cgtTBS compared to rTMS group (all patients).
3. Greater averaged and sustained clinical improvement on 17-item HDRS (averaged over 8,16 26-week follow-up) will be associated with more GABA+/Cr change across both treatment groups.
4. Greater averaged and sustained clinical improvement on 17-item HDRS (averaged over 8, 16 26-week follow-up) will be associated with lower GABA+/Cr at baseline across both treatment groups.

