5. Glx/Cr will be increased after treatment compared to baseline for treatment responders across both treatment groups (a), and Glx/Cr increase will be higher in responders than in non-responders (b).
6. Glx/Cr increase will be higher in cgtTBS compared to rTMS group (all patients).
7. Changes in depression symptoms on 17-item HDRS (16 weeks versus baseline, and 26 weeks versus baseline) will be associated with change in Glx/Cr between baseline and 16 weeks (post minus pre-treatment) in both treatment groups.

Exploratory hypotheses:

1. All the above hypotheses will be tested with other measures of depression used in the study to test robustness of findings, namely HDRS-6, BDI, PHQ-9 and QIDS-SR-16
2. GABA+/Glx changes will be associated with clinical outcomes (17-item HDRS at 16 and 26 weeks).
3. GABA+/Cr and Glx/Cr changes correlate with rAI-DLPFC net outflow changes (16 weeks vs baseline).
4. GABA+/Glx is associated with rAI-DLPFC FC and net outflow (baseline and 16 weeks) with stronger association in treatment responders after treatment compared to baseline.

5. Clinical subtypes, especially TRD severity and comorbid anxiety are associated with changes in GABA+/Cr.
6. Treatment response is associated with changes in the association between intrinsic within and between brain network FC metrics and DLPFC GABA+/Cr, Glx/Cr and GABA+/Glx levels.

Required data

- MEGA-PRESS MRS and resting-state functional MRI at baseline and, where available, at 16 weeks
- Treatment group assignment (rTMS or cgtTBS)
- Participant age, sex, and study centre and MRS protocol/platform
- For each participant, whether protocol deviations were submitted on the basis of stimulation sequence or localisation method received
- For each participant, whether there were any changes in medications in BNF Chapter 4 between baseline and 16 weeks (including starting and stopping medications)
- For each participant, whether ECT was delivered between baseline and 16 weeks
- For each participant, whether they started psychotherapy between baseline and 16 weeks
- For each participant, whether any major protocol deviations occurred from baseline to 16 weeks
- 17-item HDRS total score at baseline, 8-week follow-up, 16-week follow-up and 26-week follow-up.
- 6-item HDRS total score at baseline, 8-week follow-up, 16-week follow-up and 26-week follow-up.
- Beck Depression Inventory at baseline, 8-week follow-up, 16-week follow-up and 26-week follow-up

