- 16-item self-report Quick Inventory of Depression Symptoms (QIDS-SR-16) at baseline, 8-week follow-up, 16-week follow-up and 26-week follow-up
- 9-item Personal Health Questionnaire (PHQ-9) at baseline, 8-week follow-up, 16-week follow-up and 26-week follow-up
- Total score on the GAD-7 measure of anxiety
- Massachusetts Treatment Resistance category (mild, moderate, severe as defined in trial protocol)

Regions of interest (ROIs) / Voxel of interest (VOI)

- For MRS, a voxel (20x45x30mm) was placed on the left DLPFC based on the individual T1 anatomical image acquired prior to the MRS session.
- Grey Matter (GM), White Matter (WM) and Cerebrospinal fluid (CSF) will be parcellated through GANNET segmentation with SPM12. The GM values will be covariates of no interest in the statistical analysis.

Sensitivity analyses

In order to examine whether quality of MRS affected the results, we will conduct sensitivity analyses to

- assess a potential effect from outliers in voxel position. For this, coverage of anatomical DLPFC (in percent) and overlap with TMS brain target within the individual MRS voxels will inform through the sensitivity analysis.
- assess spectral fitting quality effects. For this, only data with higher quality data fit will be used to repeat primary and secondary hypothesis with $p < 0.1$ results.

Statistical tests

Primary Hypotheses

- The correlation between change in GABA+/Cr between baseline and 16 weeks (post minus pre-treatment) and clinical improvement will be tested by regression with the following covariates for P1 and P2:
 - *Age*
 - *Sex*
 - *Treatment group (rTMS or cgtTMS)*
 - *MGH treatment resistance*
 - *Baseline 17-item HDRS*
 - *Study centre*
 - *MRS platform (scanner/protocol)*
 - *MRS quality (GABA+ fitting error)*

$P < 0.01666$ will be the level considered for statistical significance ($p < 0.05/3$, i.e. 5% significance level with Bonferroni correction for 3 co-primary hypotheses). For missing data (e.g. due to poor spectra quality, participants' absence for the scanning or incompleteness of whole MRS sessions) we will take an available data approach, meaning individuals with enough data for a model will be included in that model's analysis.

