- For P3, a mixed effects model will be used with participant as random effect to account for three repeated measures. Each participant will contribute up to 3 repeated outcome measures to the model in addition to the baseline HDRS-17 score. The model will be adjusted for the stratification and minimisation variables: baseline HDRS-17 score, baseline Massachusetts General Hospital Treatment Resistant Depression score, and study centre as part of the covariable detailed above. For missing data, we will take an available data approach, meaning individuals with enough data for a model will be included that model's analysis.

Secondary Hypotheses

Secondary hypotheses S2, S3, S5, S6, S7 will be analysed as above, for S1 and S4 we will use a mixed model

- A Linear mixed model will be used with GABA+/Cr as the dependent variables.
- Independent variables will be the *Treatment* response group, *Time* (pre-and post) and *Treatment type*
- Covariates of no interest include
 - *Age*
 - *Sex*
 - *MGH treatment resistance group*
 - *Study centre*
 - *MRS platform (scanner/protocol)*
 - *MRS quality (GABA+/Glx fitting error respectively)*

We will take an available data approach, meaning individuals with enough data for a model will be included in that model's analysis. For secondary analyses $P < 0.05$ will be considered significant without Bonferroni correction.

The statistical analysis for primary and secondary hypotheses will be performed using a current version of either SPSS, SAS, Stata or R (for graphical illustrations). Diagnostic plots of model residuals, and the results of the Shapiro-Wilk test, will be used to determine whether variable transformations are required.

Exploratory hypotheses

Exploratory tests will be undertaken using current versions of either established advanced image analyses, SPSS, SAS, Stata or R (for graphical illustrations).

Included participants

All trial participants with baseline T1-weighted structural MRI, and MRS passing quality control criteria as detailed later in this document. We will include only participants that received the treatment to which they were assigned (that is, participants without protocol deviations on the basis of stimulation sequence or localisation method used).

Data processing

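### Co-primary P3 is stated for weeks 16 and 26, but its model takes in week 8 and specifies no week-16/26 contrast; S4, whose wording matches that pooled model, is assigned a model that cannot test it

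*SAP*

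**What the plan says.** Under Primary hypotheses, P3 reads: "Greater clinical improvement on 17-item HDRS (16 and 26-week vs baseline) will be associated with lower GABA+/Cr at baseline across both treatment groups". Two follow-up visits are named.

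Under Statistical tests, the P3 paragraph reads "For P3, a mixed effects model will be used with participant as random effect to account for three repeated measures", and then "Each participant will contribute up to 3 repeated outcome measures to the model in addition to the baseline HDRS-17 score". Baseline HDRS-17 is also listed there as an adjustment variable. The Required data section lists "17-item HDRS total score at baseline, 8-week follow-up, 16-week follow-up and 26-week follow-up" and no other HDRS-17 visit.

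Under Secondary hypotheses, S4 reads: "Greater averaged and sustained clinical improvement on 17-item HDRS (averaged over 8, 16 26-week follow-up) will be associated with lower GABA+/Cr at baseline". Its analysis is assigned by "Secondary hypotheses S2, S3, S5, S6, S7 will be analysed as above, for S1 and S4 we will use a mixed model". The mixed model set out directly below that sentence has GABA+/Cr as the dependent variable and response group, time (pre and post) and treatment type as independent variables.

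The primary threshold is 0.01666, described as "5% significance level with Bonferroni correction for 3 co-primary hypotheses". The secondary threshold is 0.05, uncorrected.

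**The concern.** P3 is one of only three confirmatory tests. Its hypothesis covers two visits and its model takes three. Baseline is counted separately from the repeated outcomes and is used as a covariate, so it cannot be the third outcome. Only week 8 is left, and P3 does not name it.

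A repeated-measures model may include a visit outside the target, provided the plan says which contrast is tested. The SAP does not. If the text is followed with a single baseline-GABA coefficient, that coefficient is an average over weeks 8, 16 and 26. P3 would then be declared supported or not on S4's question, and an analyst could settle the primary estimand after seeing the data.

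S4 adds a second problem. Its assigned model contains no averaged HDRS-17 outcome, so it has to be changed before S4 can be tested. The natural replacement is an HDRS-17 model over three visits, which is P3 as modelled, but at a threshold three times as lenient.

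**Working it through.** **1. The plan's own figure.** 0.05 / 3 = 0.016667, which agrees with the stated 0.01666. Three tests at 0.01666 sum to 0.04998; if independent, 1 − (1 − 0.01666)³ = 0.0492. The threshold is right for three tests.

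**2. Visits in P3.**
- Hypothesis: weeks 16 and 26, so two outcomes.
- Model: up to three outcomes besides baseline.
- HDRS-17 visits after baseline (Required data): weeks 8, 16 and 26.
- The three outcomes are therefore weeks 8, 16 and 26.

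**3. What a single GABA coefficient estimates.** Let b8, b16 and b26 be the baseline-GABA slopes at the three visits, and let m = (b16 + b26)/2 be P3's target, read as one averaged effect. With complete data and a participant random intercept, the single coefficient is

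(b8 + b16 + b26)/3 = (b8 + 2m)/3, which differs from m by (b8 − m)/3.

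| Assumed week-8 slope | Pooled coefficient |
|---|---|
| b8 = m | m |
| b8 = m/2 | 5m/6 |
| b8 = 0 | 2m/3 |

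The SAP gives no information on b8, so this is a range and not an estimate.

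**4. Check by simulation** (100 participants, an assumption; the true slope was set equal at all visits). With complete data the three-visit random-intercept slope was −0.27822, and regression on each participant's three-visit mean also gave −0.27822. The two-visit slope in the same data was −0.338; because the true slopes were equal, that gap is sampling variation and not bias. With 10% and 20% of visits missing, in separately simulated data sets, the three-visit slope and the regression on the mean still nearly agreed (−0.354 and −0.361; 0.164 and 0.170). The pooled P3 model therefore estimates what S4 words.

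**5. How far the two statistics can part under the null.** With equal variances and an assumed common within-person correlation ρ, the two-visit and three-visit means correlate at √{[(1 + 2ρ)/3] / [(1 + ρ)/2]}. This is 0.91, 0.94, 0.97 and 0.99 for ρ = 0.3, 0.5, 0.7 and 0.9.

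**6. S4, if it is given an HDRS-17 outcome model** (conditional; the SAP does not assign it one). A p-value between 0.01666 and 0.05 would fail as P3 and pass as S4. For a normal test statistic, the chance of that is:

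| Mean of statistic | Approximate power at 0.05 | Chance of opposite verdicts |
|---|---|---|
| 1.96 | 50% | 16.8% |
| 2.39 | 67% | 16.8% |
| 2.80 | 80% | 14.2% |
| 3.24 | 90% | 9.8% |

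If the finding were claimed by either route, the error rates over P1, P2 and this test would sum to 0.01666 + 0.01666 + 0.05 = 0.0833 (0.0814 if independent).

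**7. If P3 is taken as two separate tests** (also conditional). There are then four primary tests. The upper bound is 4 × 0.01667 = 6.7%; if independent, 1 − (1 − 0.01667)⁴ = 6.5%. Week-16 and week-26 tests of the same predictor will be correlated. Assuming the same correlation within P1/P2 and within the two P3 tests, and independence between the pairs, the familywise error is 6.2%, 5.7%, 5.4% and 4.8% for correlations of 0.5, 0.7, 0.8 and 0.9. Bonferroni for four tests is 0.05 / 4 = 0.0125.

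**The case against.** The P3 paragraph describes adjustment variables and does not claim to be a full model statement. It does not list the GABA predictor either, so the absence of a GABA-by-visit term is silence and not exclusion. A three-visit model can yield week-16 and week-26 estimates, and week 8 can add information where later visits are missing. Treatment spans 4–6 weeks, so week 8 is already after treatment and a zero association there is an extreme case. With null correlations of 0.91 to 0.99, the practical difference may be small.

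Much of this stands. The two-thirds figure is the end of a range, and the right charge is that P3's contrast is unspecified, not that it is ruled out. What remains is the plain mismatch between two named visits and three modelled ones in a confirmatory test.

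A reader might also infer that the SAP judges one and the same result at both 0.01666 and 0.05. The text does not support that: S4 is literally assigned a model with a different outcome and different predictors, which would not return P3's coefficient. The pairing of S1 with S4 could be a slip for S1 with S5, since S5 is the Glx counterpart of S1 and the covariate list mentions fitting error for GABA+ and Glx respectively. In that case S4 would fall under the models above it and the double threshold would be real, but the SAP does not say so.

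A reader might further infer that the familywise error exceeds 5%. That needs two separate P3 tests, whereas the SAP describes one model and counts three co-primary hypotheses. Even on that reading 6.7% is only a bound.

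**Conclusion.** The point holds as an inconsistency within a co-primary test. P3's hypothesis names weeks 16 and 26; its model necessarily includes week 8; no contrast ties the model back to the hypothesis. Without one, P3 would be decided on the average that S4 words, with one third of the weight on a visit outside P3. The shift is (b8 − m)/3, from nothing to a third of the effect as the assumed week-8 slope goes from equal to the later slopes down to zero.

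Separately, S4's assigned model cannot test S4. The opposite-verdict chances of roughly 10–17% apply only if S4 is moved to the HDRS-17 model its wording needs, and the error rate above 5% applies only if P3 is split into two tests. Neither is what the SAP states. All calculations beyond 0.05/3 rest on assumed sample size, correlations, missingness or power, because the SAP gives none of these.

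**What to change.** In the P3 model, name HDRS-17 at weeks 8, 16 and 26 as the outcomes and include baseline GABA+/Cr, visit, and baseline GABA+/Cr by visit. Define P3 as one contrast, the mean of the week-16 and week-26 GABA coefficients, tested at p < 0.01666. Three co-primary tests then remain and 0.05/3 stays valid. Report the visit-specific coefficients descriptively.

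Remove S4 from the model with GABA+/Cr as outcome. Either estimate it as the mean of the three visit coefficients from the same HDRS-17 model, labelled secondary and not a substitute for P3, or drop it.

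If weeks 16 and 26 are meant to be tested separately for P3, say so, count four primary tests and use 0.0125 for each.

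The cost is SAP wording and one contrast statement. Visit and GABA-by-visit take two degrees of freedom each, so the model gains four parameters, a small loss of precision.

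### As printed, the models assigned to secondary hypotheses S4 and S5 cannot test them, and the S1 model leaves its Response × Time term unstated

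*SAP*

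**What the plan says.** The list of secondary hypotheses defines S1 as a GABA+/Cr rise in responders (part a), and, as the second part, "b) GABA+/Cr increase will be higher in responders than in non-responders". S4 is a different kind of question: it takes HDRS-17 improvement "averaged over 8, 16 26-week follow-up) will be associated with lower GABA+/Cr at baseline". S5 has the same two parts as S1, with the other metabolite: "Glx/Cr will be increased after treatment compared to baseline for treatment responders across both treatment groups", and a larger rise in responders than in non-responders.

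The Secondary Hypotheses part of Statistical tests assigns the models: "Secondary hypotheses S2, S3, S5, S6, S7 will be analysed as above, for S1 and S4 we will use a mixed model". One mixed model follows: "A Linear mixed model will be used with GABA+/Cr as the dependent variables". Its predictors are given as: "Independent variables will be the *Treatment* response group, *Time* (pre-and post) and *Treatment type". Its covariate list ends with the entry "MRS quality (GABA+/Glx fitting error respectively".

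The methods that stand above this are a regression linking GABA+/Cr change to clinical improvement (P1 and P2) and a mixed model of repeated HDRS-17 scores with participant as random effect (P3). Secondary results are judged at 0.05 without correction.

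**The concern.** A hypothesis is pre-specified only if the assigned model has a coefficient or contrast that answers it. S4 and S5 appear to lack one, and for S1 the needed term is left for the analyst to supply.

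An analyst who follows the text literally would report p-values for other questions under the labels S4 and S5. One who notices the mismatch must choose a model without guidance, possibly with data in hand. For S1, leaving out the interaction would turn a question about change in responders into one about change in everybody, or about a level difference that may have existed before treatment.

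**Working it through.** The SAP gives no sample size, effect or power for these hypotheses, so there is no figure to reproduce. The check has two parts.

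**1. Match each hypothesis to its assigned model.**

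| | Needs | Assigned model | Term that answers it |
|---|---|---|---|
| S1(a) | GABA+/Cr change within responders | Mixed model, GABA+/Cr outcome | Available if the contrast is specified |
| S1(b) | Difference in change, responders minus non-responders | Same | Response × Time; not named |
| S4 | Averaged HDRS-17 improvement against baseline GABA+/Cr | Same | None: no HDRS-17 improvement, no 8- or 26-week data, baseline GABA+/Cr not a predictor |
| S5(a), (b) | As S1, for Glx/Cr | P1/P2 regression or P3 model | None: no responder group, no pre/post contrast |

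Applying the P1/P2 regression to Glx/Cr change simply reproduces S7. The P3 model has HDRS-17 as its outcome.

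The fit-error covariate is informative. S1 and S4 both concern GABA+ only, so a line naming GABA+ and Glx respectively fits a model meant for one GABA+ and one Glx hypothesis, that is, S1 and S5.

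**2. What S1 would give if only main effects were fitted.** Let p be the responder share, dR and dN the mean changes in responders and non-responders, and b the baseline difference between them. With complete pre/post pairs, a random participant effect and no covariates:

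- Time = p × dR + (1 − p) × dN
- Response = b + (dR − dN)/2
- with the interaction added, Time × Response = dR − dN, and the Time contrast within responders = dR.

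If only responders change (dN = 0, b = 0), Time = p × dR, which is 20% of dR at p = 0.20 and 40% at p = 0.40. Response = dR/2.

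A single simulated data set (100 participants, 30 responders) confirms this. The interaction model gave Time 0.072 (in non-responders), Response 0.010 and Time × Response 0.384. The formulas then predict Time = 0.072 + 0.30 × 0.384 = 0.187 and Response = 0.010 + 0.384/2 = 0.202. The fitted main-effects model gave 0.187 and 0.202.

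A simulation with assumed inputs (80 or 120 participants, 20% to 40% responders, a change or level difference of 0.5, person SD 0.7, residual SD 0.7, 2,000 runs per setting) shows how often p < 0.05 occurs. It uses the change-score and mean-score contrasts that equal the mixed-model effects in balanced data.

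| True state | Main-effects term | Specified contrast |
|---|---|---|
| Only responders rise | Time 15–59% (estimate 0.10–0.20) | Within responders 47–93%; interaction 42–78% |
| Only non-responders rise, S1(a) false | Time 73–99% | Within responders 4–5% |
| Both rise equally, S1(b) false | Time 99–100% | Interaction 4–5% |
| Stable level difference, nobody changes | Response 56–88% | Interaction 4–6% |

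These percentages illustrate the direction of the problem. They are not estimates for this trial.

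**The case against.** Four points can be made for the SAP.

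- It lists independent variables for S1 without giving a model equation. It neither says main effects only nor rules out an interaction, and S1(b) itself states a difference in change. An experienced analyst would fit the interaction. This stands: S1 is under-specified, and it cannot be said that its model fails to test it.
- S4 is the averaged-follow-up relative of P3, which already uses a mixed model. The assignment sentence may have meant a P3-type model for S4, with the bullets describing S1 alone. This is a fair reading of intent and cannot be excluded. It does not rescue the printed text, because nothing limits the bullets to S1 and no HDRS-17 model is described for S4.
- The methods above may be meant as a technique, to be used with each hypothesis's own variables. A covariate-adjusted regression of Glx/Cr change on response status would test S5(b). That is true, but response status is not in the covariate list, and S5(a), the change within responders, is still not provided for.
- These are secondary mechanistic questions, and P3 covers nearly the same ground as S4. This stands, and it limits how serious the point is.

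**Conclusion.** The assignment of S4 and S5 is wrong as printed. This follows from the text alone and needs no assumption. For S1 the model has the right outcome and factors but omits the interaction and the within-responder contrast. The 20% to 40% attenuation arises only if main effects alone are fitted, only responders change and the responder share is 20% to 40%. It also assumes complete pairs, whereas the SAP analyses available data with a fit-error covariate.

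Three stronger readings are tempting, and the document does not support them:

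- A reader might infer that S4 and S5 were simply swapped. The fit-error line makes it likely that S5 belonged with S1, but S4 may have been intended for a P3-type mixed model. Exchanging the two numbers would also not be enough, since the only stated outcome is GABA+/Cr.
- A reader might infer that S1 is analysed without an interaction. The SAP names none but excludes none.
- A reader might infer that the trial's main mechanistic conclusions are at risk. P1 to P3 have their own models and are not affected.

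This should be fixed before analysis, but it does not undermine the plan as a whole.

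**What to change.** Replace the assignment sentence with wording that covers all seven hypotheses:

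- S1 and S5: linear mixed model with participant as random effect. The outcome is GABA+/Cr (S1) or Glx/Cr (S5). Terms are Time, Response, Time × Response and treatment type, plus the listed covariates. Response is an HDRS-17 reduction of 50% or greater at 16 weeks, the visit of the post-treatment scan. Part (a) is the Time contrast within responders; part (b) is the Time × Response term.
- S4: the P3 mixed model of HDRS-17 with baseline GABA+/Cr as predictor, effect averaged over 8, 16 and 26 weeks.
- S3 and S7: regression as for P1/P2, using averaged HDRS-17 improvement (S3) or Glx/Cr change (S7).
- S2 and S6: regression of GABA+/Cr change (S2) or Glx/Cr change (S6), with treatment group as the tested term and the P1/P2 covariates.

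Amend the dependent-variable bullet to GABA+/Cr (S1) or Glx/Cr (S5); otherwise it would contradict the new text. S2 and S6 must be included because replacing the sentence would otherwise leave them with no model. The response visit is spelled out because the SAP's definition under Definitions of measures names none. The protocol, not at hand here, may already fix it, so this is a clarification.

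The cost is SAP wording only. All the data needed are already listed under Required data.

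### S3 has a three-visit HDRS-17 outcome, but the SAP does not fix which model analyses it or what happens when a visit is missing; S4 is sent to a model that does not fit it

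*SAP*

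**What the plan says.** The list of secondary hypotheses in the SAP defines S3 as follows: "Greater averaged and sustained clinical improvement on 17-item HDRS (averaged over 8,16 26-week follow-up) will be associated with more GABA+/Cr change". S4 uses the same averaged HDRS-17 outcome with a different predictor: "averaged over 8, 16 26-week follow-up) will be associated with lower GABA+/Cr at baseline across both treatment groups".

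Under Statistical tests, Secondary Hypotheses, the models are assigned by number: "Secondary hypotheses S2, S3, S5, S6, S7 will be analysed as above, for S1 and S4 we will use a mixed model". The mixed model described directly after that sentence has GABA+/Cr as dependent variable, with response group, time and treatment type as independent variables.

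Two HDRS analyses precede the sentence, both under Primary Hypotheses:

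- For P1 and P2, the relation between GABA+/Cr change and clinical improvement "will be tested by regression with the following covariates for P1 and P2".
- "For P3, a mixed effects model will be used with participant as random effect to account for three repeated measures", and "Each participant will contribute up to 3 repeated outcome measures to the model in addition to the baseline HDRS-17 score".

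The missing-data rule, given for the primary and again for the secondary analyses, is that "individuals with enough data for a model will be included in that model's analysis". Secondary tests are made at P < 0.05 without correction.

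**The concern.** S3's outcome is built from three visits, but the sentence that assigns its model sets it apart from the hypotheses that get a mixed model. S3 also shares its predictor, GABA+/Cr change, with P1 and P2. Read naturally, then, S3 is a regression with one averaged score per participant.

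On that reading, a participant with two of the three HDRS scores poses a question that the SAP does not answer. The available-data rule does not say what counts as enough data for a three-visit mean. The examples of missing data listed with the primary analyses all concern the MRS scan, not a missed HDRS visit. The analyst must either exclude the participant or average over the visits that exist. The first discards people who have a usable GABA change. The second gives different people different outcomes, and a mean of weeks 8 and 16 does not describe improvement sustained to week 26. The choice would be made with the data in hand, for a test at unadjusted 5%. The SAP already contains, in P3, an HDRS-17 model that uses every observed visit.

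**Working it through.** The SAP gives no sample size, standard deviation, between-visit correlation or missing-visit rate for S3, so there is no figure of its own to reproduce. Every numerical input below is an assumption.

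**Step 1: which model applies.**

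| Hypothesis | Outcome | Predictor | Model assigned |
|---|---|---|---|
| P1, P2 | HDRS-17 change at one visit | GABA+/Cr change | regression |
| P3 | HDRS-17, up to three follow-up measures | baseline GABA+/Cr | mixed model |
| S3 | HDRS-17 improvement, mean of three visits | GABA+/Cr change | as above (P1/P2 or P3 not stated) |
| S4 | HDRS-17 improvement, mean of three visits | baseline GABA+/Cr | mixed model with GABA+/Cr as dependent variable |

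S3 and S4 share an outcome but are assigned differently, with no reason given. The model listed for S4 does not have S4's outcome on its left-hand side.

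**Step 2: participants kept if all three visits are required.** S3 needs a week-16 scan, so take week-16 HDRS as observed. With independent missingness m8 and m26, the share kept is (1 − m8)(1 − m26).

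- 5% and 10%: 0.95 × 0.90 = 0.855.
- 10% and 20%: 0.90 × 0.80 = 0.72.
- 20% and 20%: 0.80 × 0.80 = 0.64.

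**Step 3: precision.** Information loss = 1 − (SD of slope, mixed model ÷ SD of slope, complete-visit regression)².

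First simulation: N = 90, 400 runs per setting, random-intercept SD 5, residual SD 4 (between-visit correlation 25/(25 + 16) = 0.61), true slope −2 points per SD of GABA change, visit means −6, −7, −8.

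- 10% and 20% missing: 1 − (0.594/0.655)² = 0.18 and 1 − (0.599/0.685)² = 0.24, depending on the missingness mechanism.
- 5% and 10% missing: about 12–14%.

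Further runs at N = 90 with the same two missingness patterns gave about 10–26%.

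Second simulation: n = 100, 600 runs, standardised slope −0.3, correlation 0.5 or 0.7, missing completely at random at weeks 8 and 26.

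| Missing at each of weeks 8 and 26 | Share kept | Efficiency against mixed model (correlation 0.5; 0.7) |
|---|---|---|
| 0% | 1.00 | 1.00; 1.00 |
| 10% | 0.81 | 0.78; 0.81 |
| 20% | 0.64 | 0.67; 0.64 |
| 30% | 0.49 | 0.52; 0.42 |

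**Step 4: bias when week-26 dropout depends on the week-16 score.** In the first simulation the complete-visit slope was −1.84 against −1.99 for the mixed model, about 8% too small (1.84/2 = 0.92). The further runs at N = 90 gave 7–12%. In the second simulation it was smaller. At 10% or 20% average dropout the complete-visit slopes were −0.298 to −0.300. At 30% they were −0.289 and −0.290, which is 3–4% below the true 0.3. The bias is thus not a stable figure; it varies with the assumed dropout mechanism.

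**Step 5: averaging the visits that exist.** In the second simulation the SD of the slope was within 0.001 of the mixed model's throughout, and the largest slope difference in any one run was 0.045. In the first, the information loss was about 2% or less. What changes is the outcome. With the assumed visit means, a full attender has an expected mean of (−6 − 7 − 8)/3 = −7, while someone seen only at weeks 8 and 16 has (−6 − 7)/2 = −6.5. That half point comes from attendance alone. The simulations also assumed the same slope at every visit. If the slope differs by visit, the available-visit mean weights visits by who attended.

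**The case against.** A reader might infer that the SAP rules out a mixed model for S3 and therefore drops incomplete participants or averages over unequal visits. The text does not settle that. The P3 model stands immediately before the sentence and handles repeated HDRS-17 measures, so the reference upward can reach it; on that reading S3 already gets most of what is asked. Nor does the SAP state either way of handling a missed visit. Both are consequences of one reading.

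It is also fair that regression on a per-person mean is a valid summary-measure analysis, that it gives the same slope when visits are complete, and that averaging the available visits nearly matches the mixed model for precision. The efficiency and bias figures rest wholly on assumed inputs, and participants with a week-16 scan may miss few other visits.

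P3 is an imperfect template. Its hypothesis names weeks 16 and 26 only, while its model has up to three follow-up measures, and that needs reconciling too. A mixed model for HDRS also does nothing for a missing GABA+/Cr change.

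These points limit the size of the concern. They do not remove the open choice of model, the undefined missing-visit rule, or the mismatch for S4.

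**Conclusion.** The point holds as a low-cost improvement to a secondary hypothesis. What is firm is that S3's model is not identified, that no rule covers a missing visit in the average, and that S4 is assigned a model whose dependent variable is not its outcome. That S3 is a single-score regression is the natural reading, not a stated fact.

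The harm is conditional:

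- If all three visits are required, and 5–10% of week-8 and 10–20% of week-26 scores are missing, roughly 10–25% of the information is lost. With 20% missing at both visits the loss is about a third. The slope may be attenuated by anything from almost nothing to a little over 10% when dropout depends on earlier HDRS.
- If available visits are averaged, little precision is lost but the outcome is not the same quantity for everyone.
- If visits are complete, the result does not change.

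The document does not support a claim that participants will in fact be lost or that the S3 result will be biased.

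**What to change.** State under Secondary Hypotheses that S3 uses a P3-type mixed model:

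- HDRS-17 at weeks 8, 16 and 26 as repeated outcomes, with participant as random effect;
- visit as a factor, GABA+/Cr change, and their interaction;
- the covariates already listed, including baseline HDRS-17;
- as the S3 result, the GABA-change slope averaged with equal weight over the three visits.

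Use the same HDRS-17 model for S4 with baseline GABA+/Cr as predictor. Moving S3 to the mixed model now listed for S1 and S4 would not help, because HDRS is not its outcome. While editing, align P3's hypothesis with the visits in its model, and confirm the hypothesis numbers in the assigning sentence: S5 has the same form as S1 but is listed with the other group, although that mixed model's covariates mention Glx fitting error.

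If the authors prefer the averaged score, the minimum is to say so and to define the average and the number of visits required.

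The cost is a few lines of text, the visit and interaction terms (which P3 as written does not mention), and adaptation of the P3 code. No new data are needed. The analysis relies on HDRS being missing at random, as the P3 model already does.
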